4.6 Rationale for Public Health Emergency mitigation procedures

During a Public Health emergency as declared by Local or Regional authorities i.e. pandemic, epidemic or natural disaster, mitigation procedures to ensure participant safety and trial integrity are listed in relevant sections. Notification of the Public health emergency should be discussed with Novartis prior to implementation of mitigation procedures, and permitted/approved by Local or Regional Health Authorities and Ethics Committees as appropriate.

5 Population

This study is designed for East-Asian patients aged 6 years or older with treatment-naive SAA who lack a suitable matched sibling marrow donor, or are not allogeneic transplantation candidates due to patient choice, advanced age, or infeasibility of transplantation. The diagnosis is based on objective hematological counts according to the standard Camitta criteria ([Camitta et al 1975](#)). It is estimated that at least 36 participants will be enrolled from the study sites in China, Japan, Korea or Taiwan. At least 6 pediatric participants will be recruited in total, with 3 participants from China and 3 from Japan respectively. At least one of the 6 pediatric participants in each age group (6 to 11 years old, and 12 to 17 years old) will be enrolled. For the 30 adult participants, at least 12 participants will be recruited from China to fulfill the requirements for PK profile. Replacement is not allowed in this study. The investigator or designee must ensure that only participants who meet all the following inclusion and none of the exclusion criteria are offered treatment in the study.

5.1 Inclusion criteria

Participants eligible for inclusion in this study must meet **all** of the following criteria:

1. Written study informed consent and (where applicable) assent from the participant, parent, or guardian must be obtained prior to participation in the study.
2. Participants of East Asian ancestry aged \geq 6 years old at the time of written informed consent and assent form (if applicable).
3. SAA characterized by ([Camitta et al 1975](#), [Red Blood Cell Disease \(Anemia\) 2017](#)):
 - Bone marrow cellularity < 25%, or 25-50% with < 30% residual hematopoietic cells and pancytopenia, with at least two of the following parameters in peripheral blood:

- Absolute neutrophil count $< 0.5 \times 10^9/L$
- Platelet count $< 20 \times 10^9/L$
- Absolute reticulocyte count $< 20 \times 10^9/L$

4. HSCT is not suitable or available as a treatment option (determined as per local practices or national guidelines), or has been refused by participant.

5.2 Exclusion criteria

Participants meeting any of the following criteria are not eligible for inclusion in this study.

1. Prior IST with any ATG/ALG, alemtuzumab, high dose cyclophosphamide ($\geq 45 \text{ mg/kg/day}$), CsA within 6 months, or prior thrombopoietin receptor (TPO-R) agonists
2. Participants have an Eastern Cooperative Oncology Group (ECOG) performance status (age ≥ 16 years) > 2 , or Lansky performance status (age < 16 years) < 50
3. Prior and/or active medical history of:
 - Known underlying congenital/inherited bone marrow failure or aplastic anemia (such as but not limited to Fanconi anemia, congenital dyskeratosis, congenital amegakaryocytic thrombocytopenia, or Shwachman-Diamond Syndrome)
 - Symptomatic paroxysmal nocturnal hemoglobinuria (PNH) and/or PNH clones $> 50\%$ of polymorphonuclear neutrophil or RBC at time of enrollment
 - Myelodysplastic syndrome
 - Any cytogenetic abnormalities on karyotyping or fluorescence in situ hybridization (FISH) within 30 days of study enrollment (an evaluable karyotyping with at least 10 metaphases is mandatory for eligibility)
 - Other known or suspected underlying primary immunodeficiency
 - Any concomitant malignancies that have not fully recovered from treatment or have not been disease-free for 5 years
4. Aspartate aminotransferase (AST) or alanine aminotransferase (ALT) > 3 times the upper limit of normal (ULN)
5. Creatinine $\geq 2.5 \times$ local ULN
6. Past medical history of thromboembolism within 6 months and/or prior or current antiphospholipid antibody syndrome (APS)
7. Presence of clinically active uncontrolled significant (of such severity that it would preclude the participant's ability to consent, be compliant with study procedures, tolerate protocol therapy) infection, including bacterial, fungal, mycobacterial, parasitic or viral infection, or any concurrent condition that, in the Investigator's opinion, would jeopardize the safety of the participant or compliance with the protocol
8. Any severe and/or uncontrolled medical conditions which could cause unacceptable safety risks or compromise compliance with the protocol, such as:
 - Known hepatocellular disease (e.g. active hepatitis or cirrhosis)
 - Impairment of gastrointestinal (GI) function or gastrointestinal disease that may significantly alter the absorption of study treatment (e.g., ulcerative disease, uncontrolled nausea, vomiting, diarrhea, malabsorption syndrome)
 - Active skin, mucosa, ocular or GI disorders of Grade > 1

9. Presence of hepatitis B surface antigen (HBsAg) or positive hepatitis C antibody test result at screening. A positive serology for Hepatitis B (HB) is considered as a positive test for HBsAg. In addition, if serology is negative for HBsAg but hepatitis B core antibody (HBcAb) is positive (regardless of hepatitis B surface antibody (HBsAb) status), a Hepatitis B virus (HBV) DNA test will be performed and if positive (any detectable copy of HBV DNA will be identified as "positive") the patient will be excluded
10. Positive result for human immunodeficiency virus (HIV) antibody test
11. Cardiac disorder (participants with congestive heart disease of New York Heart Association (NYHA) functional classification Grade II/III/IV (for pediatric participants, refer to the Grade II/III/IV of Modified ross heart failure classification for Children) should not be enrolled; participants with NYHA Grade II due to cardiac disorder should not be enrolled but those with NYHA Grade II due to AA may be enrolled.), arrhythmia with a risk of thrombosis (e.g. atrial fibrillation), pulmonary hypertension, or uncontrolled hypertension (>180/100 mmHg)
12. Contraindications to r-ATG or CsA, or past medical history of immediate or delayed hypersensitivity to compounds chemically similar to eltrombopag, CsA, r-ATG or their excipients
13. Participant who is unable to comprehend or is unwilling to sign an informed consent form (ICF) or assent form (if applicable)
14. Unable or unwilling to swallow tablets as per dosing schedule
15. Treatment with another investigational product within 30 days or the period 5-fold longer than the half-life of the investigational product, whichever longer, prior to the first dose of investigational treatment.
16. Pregnant or nursing (lactating) woman.
17. Woman of child-bearing potential, defined as all women physiologically capable of becoming pregnant, **unless** they are using highly effective methods of contraception while taking study treatment and for 7 days after stopping study treatment. Highly effective contraception methods include:
 - Total abstinence (when this is in line with the preferred and usual lifestyle of the participant. Periodic abstinence (e.g. calendar, ovulation, symptothermal, post-ovulation methods) and withdrawal are not acceptable methods of contraception.
 - Female sterilization (have had surgical bilateral oophorectomy with or without hysterectomy), total hysterectomy, or tubal ligation at least six weeks before taking study treatment. In case of oophorectomy alone, only when the reproductive status of the woman has been confirmed by follow up hormone level assessment.
 - Male sterilization (at least 6 months prior to screening). For female participants on the study, the vasectomized male partner should be the sole partner for that participant.
 - Use of oral, injected or implanted hormonal methods of contraception or placement of an intrauterine device or intrauterine system, or other forms of hormonal contraception that have comparable efficacy (failure rate <1%), for example hormone vaginal ring or transdermal hormone contraception.

In case of use of oral contraception woman should have been stable on the same pill for a minimum of 3 months before taking study treatment.

Women are considered post-menopausal and not of child bearing potential if they have had 12 months of natural (spontaneous) amenorrhea with an appropriate clinical profile (e.g. age appropriate, history of vasomotor symptoms) or have had surgical bilateral oophorectomy (with or without hysterectomy), total hysterectomy, or tubal ligation at least six weeks ago. In the case of oophorectomy alone, only when the reproductive status of the woman has been confirmed by follow up hormone level assessment is she considered not of child bearing potential.

If local regulations deviate from the contraception methods listed above to prevent pregnancy, local regulations apply and will be described in the ICF.

18. Sexually active males unwilling to use a condom during intercourse while taking study treatment and for 16 weeks after stopping study treatment. A condom is required for all sexually active male participants to prevent them from fathering a child AND to prevent delivery of study treatment via seminal fluid to their partner. In addition, male participants must not donate sperm for the time period specified above.

6 Treatment

6.1 Study treatment

The investigational drug for this study is eltrombopag (ETB115). The study treatment includes eltrombopag, r-ATG and CsA.

6.1.1 Investigational and control drugs

Table 6-1 Investigational and combination drugs

Investigational/Combination Drug (Name and Strength)	Pharmaceutical Dosage Form	Route of Administration	Supply Type	Supplied by
Eltrombopag (ETB115) 25mg	Tablet	Oral use	Open label participant packs; bottles	Sponsor (global)
Eltrombopag (ETB115) 12.5mg	Tablet	Oral use	Open label participant packs; bottles	Sponsor (global)
r-ATG 25mg	Sterile lyophilized powder in 10 mL vials	Intravenous use	Open label participant packs; vials	Sponsor (local)
CsA 25mg	Capsule	Oral use	Open label participant packs; blisters	Sponsor (local)
CsA 5.0g/50mL*	Solution	Oral use	Open label participant packs; bottles	Sponsor (local)

r-ATG: rabbit anti-thymocyte globulin; CsA: cyclosporine.

* The CsA solution from Sandoz is not available in China.

r-ATG and CsA will be provided locally according to the availability of each drug and dosage form.

This is an open label, single arm study, hence, no control or comparator drug is needed in this study.

6.1.1.1 Eltrombopag

For participants \geq 12 years old, eltrombopag will be initiated at a dose of 75 mg/day.

For participants \geq 6 and $<$ 12 years old, eltrombopag will be initiated at a dose of 37.5 mg/day.

Eltrombopag will be administered orally, once daily. Participants will be instructed to take eltrombopag daily with the initial dose shown in [Table 6-2](#) at the same time each day.

Table 6-2 Initial dose of eltrombopag

Age group	Initial dose of eltrombopag
For participants \geq 12 years old	75 mg/day
For participants \geq 6 years old and $<$ 12 years old	37.5 mg/day

For detailed information of food and medicine interaction, refer to [Section 6.7.2](#).

On days that PK samples are obtained, the participants should take eltrombopag during the clinic visit after the pre-dose PK samples and prior to post-dose PK samples, when instructed by the study staff.

The dose of eltrombopag will be adjusted based on platelet count, according to the criteria shown in [Table 6-3](#). The daily dose of eltrombopag will be decreased by 25 mg/day every 2 weeks (12.5 mg/day, for participants below 12 years old) if the platelet count rises above $200 \times 10^9/L$, and eltrombopag treatment will be interrupted for one week if the platelet count rises above $400 \times 10^9/L$. Once the platelet count falls below $200 \times 10^9/L$, eltrombopag should be reinitiated at a daily dose reduced by 25 mg (12.5 mg for participants below 12 years old).

Table 6-3 Dose adjustment criteria for eltrombopag

Platelet count	Dose adjustment or response
Platelet count $> 200 \times 10^9/L$ without transfusion	Decrease the dose by 25 mg every 2 weeks (by 12.5 mg for pediatric participants younger than 12 years old) Wait 2 weeks before next dose adjustment to assess the effect of the dose adjustment
Platelet count $> 400 \times 10^9/L$ without transfusion	Eltrombopag will be interrupted for at least one week until the platelet count becomes $< 200 \times 10^9/L^*$, and restarted at a dose decreased by 25 mg (by 12.5 mg for pediatric participants younger than 12 years old) (12.5 mg/day at the lowest).

* Platelet count will be assessed in absence of platelet transfusion.

Eltrombopag dose may be interrupted when clinically indicated at the discretion of the investigator. Interruptions will be reported. For participants who meet any toxicity criteria (see [Section 6.5.1](#)) or who do not tolerate the protocol-specified dosing schedule, the investigator will follow the guideline on dose modification and/or discontinuation presented in [Section 6.5.1](#).

Participants in whom the treatment is assessed as effective at Week 26 may continue treatment with eltrombopag and CsA after Week 26 (in the extension part of the study). Eltrombopag will

be provided for the participants who entered the extension part and are considered to require continued treatment up to Week 52.

If participants have achieved their best hematological response (no increase in ANC, hemoglobin or platelet occurs within 8 consecutive weeks) in the extension part and all the hematologic criteria (platelet count $>50 \times 10^9/L$, hemoglobin level $>100 \text{ g/L}$, and ANC $>1.0 \times 10^9/L$ unaided by transfusions and growth factors) remain fulfilled for at least 8 consecutive weeks, the dose of eltrombopag will be tapered according to [Table 6-4](#). Maintenance of the dose is permitted if, in the opinion of the investigator, a participant is deemed to be placed at a safety risk (such as, but not limited to, bleeding or severe infections) at the decreased dose.

Table 6-4 Dose adjustment criteria in extension part after Week 26 (for participants maintaining hematologic response for more than 8 weeks)

Criteria	Dose adjustment or response
a) Achieved the best hematological response* and all the hematologic criteria (platelet count $> 50 \times 10^9/L$, hemoglobin level $> 100 \text{ g/L}$, and ANC $> 1.0 \times 10^9/L$) remain fulfilled.	Decrease by 50% (see Table 6-5). Continue monitoring hematology every 2 weeks.
b) After 8 weeks at this decreased dose if the hematological response is maintained and all the hematologic criteria (platelet count $> 50 \times 10^9/L$, hemoglobin level $> 100 \text{ g/L}$, and ANC $> 1.0 \times 10^9/L$) remain fulfilled	Interrupt eltrombopag. Continue monitoring hematology every 2 weeks.
For CR participants: While at the decreased dose a) or interruption b), blood counts drop to that do not meet CR criteria at 2 serial blood counts at least one week apart (not explained by another clinical process) For PR participants: While at the decreased dose or interruption, drop to platelet counts $< 30 \times 10^9/L$ or Hb $< 90 \text{ g/L}$ or ANC $< 0.5 \times 10^9/L$ or need transfusion	Can increase to the dose before decrease or restart at the dose before interruption. Continue monitoring hematology every 2 weeks.

*No increase in ANC, hemoglobin or platelet count occurs within 8 consecutive weeks
Hematological value will be assessed in the absence of platelet transfusion, RBC transfusion and G-CSF.
If response has been achieved before Week 26 and maintained, the dose will be decreased no sooner than Week 26.

Table 6-5 Dose decrease of eltrombopag after Week 26

Dose before decrease	50% decreased dose
75 mg/day	37.5 mg/day
50 mg/day	25 mg/day
37.5mg/day	25mg/day or 12.5mg/day*
25 mg/day	12.5mg/day
12.5mg/day	12.5mg/every other day

* When eltrombopag dose need to be reduced by 50% from 37.5 mg/day, the investigators will need to select an appropriate dose level (choose either 25 mg or 12.5 mg daily for participants treated with eltrombopag 37.5 mg/day) according to participants' clinical status

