6.1.5 Treatment duration

The core treatment part of this study is 6 month from the start of eltrombopag treatment (Day 1 to Week 26). Participants assessed as responders at Week 26 will be eligible to enter the extension part and may continue treatment with eltrombopag and CsA after Week 26 until Week 52.

Core treatment part

The planned duration of eltrombopag treatment is 6 months in the core treatment part. Participants may be discontinued from treatment earlier due to unacceptable toxicity, disease progression and/or treatment is discontinued at discretion of the investigator or of the participant (see [Section 9.1.1](#)).

The administration of r-ATG will be from Day 1 to Day 5.

For all participants, CsA will be administered at doses that obtain the target trough level range for 6 months if well tolerated. CsA dose may be interrupted temporarily when clinically indicated at the discretion of the investigator or treating physician. The parenteral route of administration may be used temporarily for CsA administration if indicated. Temporary interruptions for transient toxicities or dose adjustments will be reported. Per protocol interruptions will not be reported as deviations.

Extension part

The participants assessed as responders at Week 26 are eligible to enter the extension part. Eltrombopag will be provided up to Week 52 for the participants who enter the extension part and are considered to require continued treatment. For the participants who meet the discontinuation criteria in [Section 9.1.1](#), the study treatment will be discontinued.

In extension part, CsA will last for at least 18 months after Week 26 if well tolerated (total duration is from Day 1 to at least Year 2). CsA will be maintained or tapered based on the discretion of the investigator according to local practice. It is recommended that CsA treatment dose last for at least 3 months after achieving the best hematologic response, and after that CsA is recommended to be tapered by 0.3 mg/kg every month or 1 mg/kg every 3 months. CsA dose may be decreased or interrupted temporarily when clinically indicated at the discretion of the investigator or treating physician. Temporary interruptions for transient toxicities or dose adjustments will be reported. Per protocol interruptions will not be reported as deviations. After Year 2 (Week 104), CsA administration will be at the discretion of the investigator, and will not be provided within the trial anymore.

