6.1.5.1 Treatment beyond disease progression

Study treatment beyond disease progression is not applicable for this study because the participant should discontinue the study treatment once assessed as non-responder at Week 26 or relapse at any time, due to the discontinuation criteria in [Section 9.1.1](#). Other treatments can rely on investigator's discretion or refer to treating physician after disease progression.

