6.5 Dose escalation and dose modification

6.5.1 Dose modifications

The eltrombopag dose adjustment based on treatment response are in [Section 6.1.1.1](#).

For participants who do not tolerate the protocol-specified dosing schedule, dose interruptions, and/or reductions are either recommended or mandated in order to allow participants to continue the study treatment. Deviations to mandatory dose interruptions and/or reductions are not allowed.

Permanent treatment discontinuation is mandatory for specific events indicated as such in [Section 9.1.1](#).

These dose changes must be recorded on the Dosage Administration Record – electronic case report form (eCRF).

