Improvement in counts that are dependent upon exogenously administered growth factors or transfusion will not be considered as fulfilling response criteria.

The exclusion period of these therapies are detailed below:

- Platelet transfusions: 7 days preceding the assessment of platelet count
- Packed RBC transfusions: 14 days preceding the assessment of hemoglobin
- Growth factors: 21 days preceding the assessment of response

No response (NR) is defined as not fulfilling the response criteria.

Transfusion independence at each assessment point is defined as follows:

- Platelet transfusion independence: The participants who are transfusion dependent at baseline become transfusion free for a period of at least last 4 weeks.
- RBC transfusion independence: The participants who are transfusion dependent at baseline become transfusion free for a period of at least last 8 weeks.

Clinical relapse is considered as the occurrence of any of the following event in a participant who had achieved a hematological response (CR or PR) but has subsequently lost response (not explained by any other independent concomitant medical conditions):

- meeting again the criteria for SAA
- requirement for transfusion again for participants who had been transfusion independent
- decrease in any of the peripheral blood counts to: absolute neutrophil count $< 0.5 \times 10^9/L$ or platelets $< 20 \times 10^9/L$.

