9.1 Discontinuation

9.1.1 Discontinuation of study treatment

Discontinuation of study treatment for a participant occurs when study treatment is permanently stopped earlier than the protocol planned duration and can be initiated by either the participant or the investigator.

The investigator must discontinue study treatment for a given participant if, he/she believes that continuation would negatively impact the participant's well-being.

Study treatment must be discontinued under the following circumstances:

- The hematologic response is assessed as NR at Week 26.
- Diagnosis of relapse.
- Participant/guardian decision.
- Pregnancy.
- Any of the following is observed: a new clinical significant morphological, chromosomal or cytogenetic abnormality*, diagnosis of myelofibrosis^{**} or progression to MDS or AML.
- Participant meets any of the stopping criteria in [Section 6.5.1](#).
- Any laboratory abnormalities that in the judgment of the investigator, taking into consideration the participant's overall status, prevents the participant from continuing the study treatment.
- Use of prohibited treatment as per recommendations in the prohibited treatment section (see [Section 6.2.2](#)).
- The participant is withdrawn from the treatment with planned r-ATG or CsA, or the participant cannot tolerate the planned study treatment (e.g. Infusion-related r-ATG reactions refractory to all appropriate supportive measures; Life threatening acute hypersensitivity reactions).
- The participant has an unacceptable AE whose causal relationship with eltrombopag cannot be ruled out.
- The participant is found to be significantly non-compliant with the requirements of the protocol (including treatment non-compliance).
- The investigator (or sub-investigator) believes that the participant will not benefit from eltrombopag or
- that the participant needs to transfer to other therapy (e.g. HSCT, ATG/ALG).
- The study is prematurely terminated.
- Any situation in which study participation might result in a safety risk to the participant.

*: Discontinuation should be considered if any new chromosomal or cytogenetic abnormality is observed, and if considered significant should be discontinued. This also applies for participants that started treatment based on normal karyotyping while FISH results were not yet available.

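### For PR participants on the eltrombopag taper, Table 6-4 permits a restart at falls that Section 8.3 calls relapse and Section 9.1.1 makes a permanent stop, and the final SAP can then show one participant as both Week 52 responder and relapse

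*Protocol*

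**What the plan says.** Counts below are ×10⁹/L; hemoglobin (Hb) is in g/L.

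- **Restart rule (Protocol 6.1.1.1, Table 6-4).** A participant at the halved dose or off drug may go back when counts fall: "Can increase to the dose before decrease or restart at the dose before interruption". For PR participants the triggers are platelets <30, Hb <90, ANC <0.5 or need for transfusion. For CR participants the trigger is an unexplained loss of CR on two serial counts at least a week apart.
- **Relapse (Protocol 8.3).** The participant must have had CR or PR "but has subsequently lost response (not explained by any other independent concomitant medical conditions". Any one of three events then qualifies: SAA criteria met again; "requirement for transfusion again for participants who had been transfusion independent"; or "decrease in any of the peripheral blood counts to: absolute neutrophil count" <0.5 or platelets <20.
- **Stop rule.** Section 9.1.1 lists "Diagnosis of relapse" among the circumstances in which study treatment must be discontinued, and defines discontinuation as permanent. Section 6.1.5.1 says "the participant should discontinue the study treatment once assessed as non-responder at Week 26 or relapse at any time". Section 6.1.5 applies this to the extension part, where the taper takes place: "For the participants who meet the discontinuation criteria in" Section 9.1.1, study treatment ends. Section 6.5.1 adds "Permanent treatment discontinuation is mandatory for specific events indicated as such in" Section 9.1.1. None of these exempts the taper.
- **Final-analysis SAP (11-Nov-2024).** In 2.7.1, Week 52 and yearly response is by investigator assessment, and participants who relapse are reported as relapsed at all later response assessments. For duration of response, 2.7.1 derives relapse by program from one blood count. In 2.7.3, only responders without relapse are censored.

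**The concern.** The same event in a PR participant on the taper attracts two instructions: the drug may be restarted, and study treatment must stop for good. Two investigators could handle identical participants differently. One restarts. The other diagnoses relapse, stops study treatment (which includes CsA) and ends efficacy assessments under Section 9.1.1.

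The analysis can inherit the split. If the investigator restarts and does not record relapse, the participant can count as a responder at Week 52, while the program counts the same fall as a relapse in duration of response. At stake is the agreement between two secondary results in one report from a 36-participant study meant to support registration.

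**Working it through.** **1. Triggers side by side, PR participants, unexplained fall unless stated.**

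| Event on the taper | Table 6-4 | Section 8.3 | Conflict |
|---|---|---|---|
| ANC <0.5 | restart allowed | relapse | yes |
| Platelets <20 (inside <30) | restart allowed | relapse | yes |
| Transfusion again after independence | restart allowed | relapse | yes |
| Platelets 20 to <30 only | restart allowed | not relapse | no |
| Hb <90 only | restart allowed | not relapse | no |
| Any of these, explained by another condition | restart allowed | not relapse | no |

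**2. CR participants.** The trigger needs two serial counts, at least a week apart, that no longer meet CR. The overlap arises only when the fall is confirmed in this way and reaches relapse level. Transfusion alone is not a listed CR trigger.

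**3. Does the lost-response condition remove the conflict?** Take ANC <0.5, platelets <20 and reticulocytes <20 as each present or absent: 2³ = 8 patterns. Two have neither low ANC nor low platelets, which leaves 6 that meet a PR trigger.
- If any listed event is itself a loss of response, 6 of 6 are relapse.
- If the 2-of-3 response in Section 8.3 must also be lost, the two isolated falls (ANC only, platelets only) drop out, leaving 6 − 2 = 4 of 6. This reading makes the third relapse criterion redundant.

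The conflict survives both readings. These are patterns, not frequencies.

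**4. What the final SAP does with such a fall.**
- Duration of response: an event by program, whether or not drug is restarted, and not censored.
- Week 52 and yearly response: whatever the investigator assessed, unless relapse is carried forward. The carry-forward sentence does not say whether it uses relapse recorded by the investigator in the eCRF (Protocol 8.3) or programmed relapse.

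**5. Time available.** The Table 6-4 footnote allows a taper from Week 26, giving at most 52 − 26 = 26 weeks before study eltrombopag ends. If the 8-week plateau must fall within the extension part (Section 6.1.1.1), the taper starts at Week 34, giving 52 − 34 = 18 weeks.

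**6. Size.** The plan's own precision table reproduces with Clopper-Pearson limits at n = 36: 14/36 gives (23.1, 56.5), 16/36 gives (27.9, 61.9), 18/36 gives (32.9, 67.1), and the maximum half-width is 17.1 points. One participant classed the other way moves a rate by 1/36 = 2.8 points, provided counts meet response at that visit; otherwise by 0.

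The documents do not give a number of restarts or a Week 52 rate. Purely as illustration, assume 20/36 responders:

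| Reclassified | Rate | 95% CI |
|---|---|---|
| 0 | 55.6% | 38.1, 72.1 |
| 1 | 52.8% | 35.5, 69.6 |
| 3 | 47.2% | 30.4, 64.5 |

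**The case against.** **The protocol already gives an answer.** A permission yields to a mandatory stop, so relapse ends treatment, and the restart row keeps real uses: platelets 20 to <30, Hb <90, loss of CR short of relapse, and explained falls in PR participants. This is a fair reading and the one the fix adopts. It does not remove the defect. Unless the 2-of-3 reading in step 3 is taken, the ANC <0.5 trigger has no use for an unexplained fall, and nothing in the table warns the investigator.

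**Few participants can reach the overlap.** Taper entry needs platelets >50, Hb >100 and ANC >1.0 for at least 8 weeks, while CR needs platelets >100 with the same Hb and ANC limits. PR participants who enter the taper are therefore essentially those with platelets above 50 and up to 100. Counts are taken every 2 weeks, so the harmless triggers may often act first. This stands, and it is a main reason for the low severity.

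**Context names the relapse source.** The carry-forward sentence sits in a section based on investigator assessment, so investigator relapse is the natural reading. Final SAP 2.7.2 will also list investigator and programmed responses together. Both points have weight. But on that reading the rates and duration of response can still disagree about the same participant, and a listing shows the disagreement without settling it.

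**A stronger reading to avoid.** A reader might infer that the final SAP says nothing about how restarts count. For duration of response that is not so: 2.7.1 and 2.7.3 make the fall an event regardless of restart.

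**Conclusion.** The conflict holds for PR participants, and for CR participants only when a relapse-level fall is confirmed on two serial counts. The analysis gap is confined to Week 52 and yearly response, where the source of carried-forward relapse is not named and the result can disagree with duration of response.

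Three further inferences are not supported. The primary endpoint is not at risk, since no taper starts before Week 26. The whole restart row is not in conflict, as step 1 shows. And no count of affected participants can be read from the documents; it may be zero.

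The effect is 2.8 points per reclassified participant on a descriptive secondary rate, assuming all 36 are in the denominator and counts meet response at the visit in question. The clinical consequence is also bounded: study eltrombopag ends by Week 52 in any case, and Section 6.1.5.1 leaves treatment after relapse to the investigator. Severity: minor.

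**What to change.** 1. **Protocol Table 6-4, restart row:** add *unless relapse per Section 8.3*. The restart then agrees with the mandatory stop. Amendment 3 (22-Dec-2021), which set out to remove inconsistencies, was a suitable place. Exempting the taper from relapse instead would be a clinical choice for the sponsor and is not requested; Section 8.3.1 ties the efficacy measurements to the pivotal study.
2. **Final-analysis SAP 2.7.1:** name the relapse source that drives the carry-forward for Week 52 and yearly response. Count restarts at relapse-level counts, or on renewed transfusion after independence, as relapsed there, so that the rates agree with duration of response. If any such restarts occurred, add one sensitivity run with them classed the other way.

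Timing: the last first visit was 03-Dec-2021. Assuming 0 to 30 days to Day 1, the last Week 52 visit (Day 365 plus 7 days) falls between 09-Dec-2022 and 08-Jan-2023. By the final SAP, therefore, only change 2 can act.

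Cost: one phrase, one SAP paragraph and at most one extra run. No new eCRF field or visit is needed, because dose changes, counts and transfusions are already recorded. The downside is that Week 52 and later response rates may come out slightly lower.
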